7.3 Sensitivity analyses

7.3.1 Sensitivity to missing data

Participants will be unable to submit any questionnaire with any missing fields when an online version of case report forms (CRFs) are used. Therefore, there will be no missing data from questionnaires completed online. This will be clearly explained in the information sheet. There may be some missing data when participants choose to use paper CRFs. Also, some missing data may result from loss to follow-up. A small percentage (5% or less) of missing data is generally inconsequential in which case we will carry out analysis of available data without imputation. For both the primary and secondary outcomes the extent and possible patterns of missing data will be checked. The relationship between baseline variables and missing primary outcome data will be examined. Additional data analysis will be undertaken in the event of missing data in the primary outcome and/or baseline covariates being more than 5%. A sensitivity analysis using multiple imputation will be considered to minimise potential bias affecting estimated treatment effect. Factors to include in the imputation model will be those that are likely to be related to the outcomes and those related to missingness. The imputation model will include the variables of the analytical model [26,27].

7.3.2 Sensitivity to inadequate compliance

As stated earlier, a CACE analysis will be performed to assess whether the estimated treatment effect from the primary analysis is influenced by inadequate (< 80%) compliance. The CACE analysis will be based on the comparison of the outcome measure between the observed compliers in the intervention (iACT4CARERS plus TAU) arm and the "would be" compliers in the control (TAU alone) arm. The "would be" compliers group is a counterfactual (or, unobserved) group, predicted probabilistically as those in the control group who would have complied had they been offered the intervention.

The CACE estimation will be implemented using the generalised structural equation modelling **(gsem)** procedure in Stata [28]. The gsem framwork for CACE estimation will encompass two models: (i) a linear model for the outcome with a Gaussian family and identity link function, and (ii) a latent class model with logit link for probabilistic prediction of compliance. The potential predictors of compliance in the latent class model will include information collected on extra-trial treatments, treatment expectation, treatment preference along with baseline GAD-7 severity and ethnicity.

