6.3.1.3 Participant Exclusion Criteria

- Lacking capacity to provide fully informed written consent: The capacity to consent to participate in the study will be assessed and recorded using a Mental Capacity ACT (2005) assessment tool developed by Norfolk and Suffolk NHS Foundation Trust. Participants will not be included in the study if they are unable to provide this.
- 2) Currently receiving ongoing formal psychological therapy: Participants will be asked to report any ongoing treatment they are receiving from healthcare services during the screening session. Participants currently receiving formal psychological therapy such as CBT, psychodynamic psychotherapy, systemic therapy and counselling will be excluded.
- 3) Experiencing disabling medical or mental health problems making participation inappropriate or impractical: Participants will be asked to report any ongoing untreated condition during the screening session. Following the baseline assessment, the participant's GP will be informed of their involvement in the study, and any concerns raised by their GP regarding their involvement will be followed by a full discussion with the participant.
- 4) Expressing active suicidal intent: The risk of suicide will be assessed during the screening session. This will be assessed using the suicide risk assessment protocol co-developed with Norfolk and Suffolk NHS Foundation Trust. This protocol has been used across multiple studies run by our team. Those presenting suicidal ideation with active intent will be excluded.

Potential participants with insufficient understanding of English to complete screening measures and engage in the intervention will be encouraged to bring a family member or a friend who can support the participant and act as an interpreter. This approach was recommended by PPI members from ethnic minority groups. If this option is not available, a professional interpreter can be arranged through the third company, which UEA already has a contract in place. If the study team needs to directly contact another family member or an interpreter regarding the participant such as arranging the appointment, verbal consent will be obtained from the participant for doing so.

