6.4.2 Arm B (Control)

6.4.2.1 Treatment-as-Usual (TAU)

The control is TAU alone. Participants in either group will continue to receive any routine support, such as Admiral Nurse appointments, during the trial. They will not be discouraged from seeking treatment outside of the study for ethical reasons. As per NICE guideline [NG97], TAU for carers normally consists of information, brief education, practical advice, local carer support groups and/or respite care provided by health and social care services, or relevant charities based on the needs. TAU will be monitored using a modified Client Service Receipt Inventory (modified CSRI[31]). We will not withdraw participants if they start receiving formal psychological therapy such as CBT, psychodynamic psychotherapy, systemic therapy and counselling during the trial, but this information will be monitored using the modified CSRI. We will undertake additional exploratory data analysis to assess the impact of contamination if a substantial proportion of participants have used pharmacological or psychological therapies.

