6.10.4 Statistical Methods

6.10.4.1 *Outcomes*

In the primary analysis, which will be by intention to treat, linear mixed models with random intercepts for site and therapist will be used to estimate group differences in total score on GAD7. Score at 12- and 24-week follow-ups will be used as the dependent variables. The treatment group will be used as the independent variable. Baseline outcome score, the research site and ethnicity will be used as the covariates. Sensitivity analyses will be used to identify any variations or methods (e.g. outliers, therapists, the number of sessions completed) that may influence the findings. Secondary outcome measures will be analysed in a similar fashion to the primary outcome measure. The impact of contamination due to non-compliance as well as participants receiving treatments that are not part of the trial (e.g. psychological therapy, pharmacological therapy) will be assessed by using CACE analysis where information on any extra-trial treatments will be incorporated as covariates in the CACE approach.

Statistical significance will be set at the conventional (2-tailed) 5% level and all parameter estimates will be presented with 95% confidence intervals. Analyses will be carried out by the trial statistician blinded to group allocation.

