7.1.2 Secondary outcomes

Clinical outcomes

- Patient Health Questionnaire-9 (PHQ-9 [18]): A 9-item self-report questionnaire assessing the severity of depressive symptoms. Both GAD-7 and PHQ-9 are used routinely in NHS psychological services for assessing recovery.
- Comprehensive Assessment of Acceptance and Commitment Therapy processes (CompACT [19]): A 23-item self-report questionnaire assessing psychological flexibility, which is commonly used in ACT studies. The total score and three subscale scores (Openness to Experience, Behavioural Awareness and Valued Action) will be used.
- Experiential Avoidance in Caregiving Questionnaire (EACQ [20]): A 15-item self-report questionnaire assessing experiential avoidance (one component of psychological flexibility) in the caregiving context. The total score and three subscale scores (Active Avoidant Behaviours, Intolerance of Negative Thoughts and Emotions Towards the Relative and valued action and Apprehension Concerning Negative Internal Experiences Related to Caregiving) will be used.
- Satisfaction With Therapy and Therapist Scale-Revised (STTS-R [21]): A 12-item self-report questionnaire assessing satisfaction with therapy and satisfaction with the therapist. The subscale scores (Satisfaction with therapy subscale, Satisfaction with the therapist and Outcome/Global improvement) will be used.

Cost-effectiveness measures (mainly to be used for a health economic analysis)

- EQ-5D-5L [22]): A 5-item self-report questionnaire assessing health-related quality of life.
- ICEpop Capability measure for Older people (ICECAP-O [23]): A 5-item questionnaire assessing capabilities that are required to have a high quality of life in older adults.
- Modified Client Service Receipt Inventory (modified CSRI [24]): An interview-based measure of health and social care service utilisation. This scale will be used to monitor TAU received in both arms during the trial and to calculate patient costs.

Potential Sources of bias

Expectations about treatment and participants' intervention arm preference are potential sources of bias that can affect treatment outcomes. These measures will be collected during the baseline session prior to randomisation, after participants are given a rationale for iACT4CARERS.

- Expectations about treatment: Two questions asking how much participants expect their symptoms and life to improve if they receive iACT4CARERS will be used (collected on a five-point Likert scale from 0 to 4).

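### The CACE model may predict compliance from extra-trial treatment taken up after randomisation, which may misidentify would-be compliers in the TAU arm and bias the complier effect in either direction

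*SAP*

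**What the plan says.** SAP 5.2 calls for a CACE analysis if compliance, defined as six or more online sessions, is below 80%. SAP 7.3.2 specifies a linear outcome model joined to a logit latent class model. Class membership is observed in the intervention arm and predicted in the TAU arm. On the predictors it says: "The potential predictors of compliance in the latent class model will include information collected on extra-trial treatments". The list continues with treatment expectation and preference, "along with baseline GAD-7 severity and ethnicity". For expectation and preference, SAP 7.1.2 states: "These measures will be collected during the baseline session prior to randomisation". No measurement time is given for extra-trial treatments.

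Protocol 6.10.4.1 gives the purpose. The CACE is to assess contamination, including psychological or drug treatment outside the trial, and "information on any extra-trial treatments will be incorporated as covariates in the CACE approach".

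Three further passages bear on timing:
- Protocol 6.3.1.3 bars psychological therapy at entry: "Participants currently receiving formal psychological therapy such as CBT, psychodynamic psychotherapy, systemic therapy and counselling will be excluded".
- Protocol 6.4.2.1 allows it afterwards: "We will not withdraw participants if they start receiving formal psychological therapy". Of both arms it also says: "They will not be discouraged from seeking treatment outside of the study for ethical reasons".
- Protocol 6.10.5 administers the modified CSRI (the service-use inventory that records such treatment) at baseline, 12 and 24 weeks.

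**The concern.** Would-be complier status is a trait fixed before allocation. Randomisation makes its distribution the same in both arms given any baseline variable, so a class model learned in the intervention arm can be applied to TAU. A variable measured after randomisation carries no such guarantee. Its relation to compliance can differ between arms, and the model then applies the intervention-arm relation where it is wrong.

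There is reason to think this could happen here. Participants are seeking help for anxiety, TAU participants have no contact with trial therapists, and either arm may look for care elsewhere. If TAU participants who would have completed the programme seek therapy because they did not receive it, while users of outside therapy in the intervention arm are mostly non-completers, the model will treat those TAU participants as probable non-compliers. If the more anxious seek therapy, the predictor also carries outcome information into the class model.

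The CACE would be read as the effect in those who complete treatment. It is also the method protocol 6.10.4.1 names for contamination.

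**Working it through.** **The plan's own figures.** The documents give no figure for the CACE. The sample size is not in question: a two-sample t-test at d = 0.35, two-sided 5% and 90% power needs 172.5, so 173 per arm; 173/0.7 = 247.1, so 248 per arm and 496 in total, as stated.

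**Timing of the predictors**

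| Predictor in SAP 7.3.2 | Timing in the documents |
|---|---|
| GAD-7 severity | labelled baseline |
| Ethnicity | collected at baseline (SAP 4.2) |
| Expectation, preference | before randomisation (SAP 7.1.2) |
| Extra-trial psychological therapy | starts after entry (excluded at entry, allowed later) |
| Extra-trial medication | may predate entry; CSRI wave not stated |

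**How misidentification arises.** Assume 68.5% compliers. Let 5% of compliers and 25% of non-compliers use outside treatment in the intervention arm, and 25% of both classes in TAU.
- Learned P(complier | use) = 0.685×0.05 / (0.685×0.05 + 0.315×0.25) = 0.03425/0.113 = 0.303. The true value in TAU is 0.685.
- Learned P(complier | no use) = 0.685×0.95 / (0.685×0.95 + 0.315×0.75) = 0.65075/0.887 = 0.734.
- Implied complier share in TAU = 0.25×0.303 + 0.75×0.734 = 0.626, against a true 0.685.

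The full model also uses the outcome, which recovers a little: the simulated share was 0.637.

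**Effect on the CACE: uptake differs by arm but is not driven by symptoms.** These are large-sample EM fits of a two-class Gaussian model with no treatment effect in non-compliers (40,000 per arm, 3 replicates). All inputs are assumed. The direct complier effect is -0.5 SD and the outside treatment works (-0.4 SD). True CACE = -0.5 + (-0.4)×(complier uptake in intervention - complier uptake in TAU); in the moderate case, -0.5 + (-0.4)×(0.05 - 0.25) = -0.42.

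| Complier uptake, TAU vs intervention | True | Outside treatment in class model | Baseline predictors only | Error with outside treatment |
|---|---|---|---|---|
| 15% vs 15% (non-compliers also 15%) | -0.50 | -0.490 | -0.494 | about 2% too small |
| 15% vs 10% | -0.48 | -0.507 | -0.478 | 0.027/0.48 = 6% too large |
| 25% vs 5% | -0.42 | -0.537 | -0.419 | 0.117/0.42 = 28% too large |
| 40% vs 5% | -0.36 | -0.558 | -0.364 | 0.198/0.36 = 55% too large |

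Putting outside treatment in the outcome model as well does not cure the last two rows (-0.507 and -0.521). If it has no effect on GAD-7, the 25% vs 5% case is almost unbiased (-0.502 against -0.50) although classes are still misassigned. With baseline predictors only, the fit stayed within 0.006 of the Wald estimate in every scenario.

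**Effect on the CACE: uptake driven by symptoms.** Separate fits of the same kind, all inputs assumed (about 70% compliers; complier effect -2.0 before any outside treatment):
- Symptom-driven uptake (compliers 23% TAU, 9% intervention), treatment without effect: -1.49 against -2.00, so 0.51/2.00 = 26% too small. Baseline predictors only: -2.03.
- Arm acts on uptake only through symptoms (23% vs 18%), treatment without effect: -1.78 against -2.00, 11% too small.
- Uptake not symptom-driven, treatment works: -2.07 against -1.78, so 0.29/1.78 = 16% too large. Baseline predictors only: -1.80.
- Symptom-driven uptake and effective treatment together: -1.69 against a Wald estimate of -1.75, about 3% too small. The two biases largely offset.

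**The case against.** The SAP speaks of potential predictors and names no CSRI wave. Because the CSRI is also taken at baseline, a pre-randomisation reading is available for medication, so it would go too far to say that all extra-trial treatment is post-randomisation. That stands for medication. It does not rescue psychological therapy, and the protocol's contamination purpose points to treatment during the trial.

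A reader might infer that uptake is changed by allocation and that the CACE is therefore biased by a known amount. No passage says uptake differs by arm. The uptake rates and the symptom-driven mechanism are assumptions, and the direction reverses between plausible mechanisms. SAP 7.3.2 also does not list the outcome-model covariates or state that non-compliers have no effect, so the fits represent one natural form of the model. These points limit the claim to a conditional one.

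A reader might also take the CACE for the plan's only look at non-compliance. It is not: SAP 6.5 summarises sessions completed, SAP 7.4 correlates them with GAD-7 in the intervention arm, and protocol 6.10.4.1 lists them among its sensitivity factors. None of these is a randomised comparison, however. Nor does the 70% green threshold in protocol Table 1 forecast that the CACE will run. It is a progression minimum, and shows only that a trial progressing as planned could fall below 80%.

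Finally, dropping the variable has a price. Where it is related to compliance but not to arm, it improved the correlation between predicted and true class slightly (0.413 to 0.449). With the 25% vs 5% arm difference, it lowered that correlation from 0.418 to 0.300.

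**Conclusion.** The specification weakness is real and should be fixed. A class that must be fixed at baseline is predicted from information with no baseline restriction, part of which necessarily arises after entry. The resulting bias is possible but not demonstrated. It requires uptake to depend on allocation, compliance or evolving symptoms, and its size and direction cannot be derived from the documents. Under assumed inputs it runs from roughly 25% too small to 15% or more too large, reaching 55% in the most extreme case tried. It is near zero when uptake is unrelated to arm, compliance and symptoms. Because the sign is unknown, readers could not correct for it afterwards.

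The stronger reading, that the planned CACE is certainly wrong or that the trial's main result is compromised, is not supported. The CACE is a conditional sensitivity analysis; the primary intention-to-treat comparison and the sample size do not depend on it.

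**What to change.** In SAP 7.3.2, limit the compliance-class predictors to variables measured before randomisation: baseline GAD-7, ethnicity, treatment expectation, treatment preference, and service use or medication from the baseline CSRI, with the wave named. Remove extra-trial treatment started after randomisation from the CACE model.

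Tabulating that treatment by arm is needed but not enough, because protocol 5.1.1, 6.4.2.1 and 6.10.4.1 undertake to assess the impact of contamination. Add a separate analysis under SAP 7.4, labelled exploratory and not to be read as a randomised comparison. Align protocol 6.10.4.1 with this.

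The cost is a small wording change in the SAP and protocol (the latter through the amendment route in protocol 7.4), one extra exploratory analysis, and possibly slightly weaker class prediction if outside treatment turns out to be unrelated to arm. No new data are needed.

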7.3.3 Sensitivity to referral routes

This sensitivity analysis will be carried out if the distribution of participants from the two referral routes (self-referred and health care staff referred) differs between the two intervention arms at baseline. The analysis will define the referral route variable based on the referral site information. Participants whose source of referral is recorded as UEA are all self-referred, while those recorded as one of the 20 NHS sites are health care staff referred. This information is recorded in the referral_site variable in the Referral form in REDCap. Any potential confounding bias in the estimated treatment effect due to referral route will be assesses by including a binary indicator of the referral route (0=self-referred, and 1= health care staff referred) in the primary ITT analysis model as an additional covariate.

7.3.4 Sensitivity to treatment expectation/treatment preference

Similar to the sensitivity analysis of referral routes, baseline balance of treatment expectation and treatment preference measures will be assessed via descriptive statistics. If a difference is observed at baseline, any potential confounding bias by these variables will be accounted for in the ITT analysis model by including them as additional covariates.

7.4 Additional exploratory analyses

The following exploratory analyses will be carried out considering factors that may influence the finding (therapist fidelity, the number of sessions completed, change in psychological flexibility).

- **Therapist fidelity:** The ACT-FM produces ACT consistency and inconsistency scores for each therapist. Therapist response time will be collected for each participant for every session. Descriptive statistics will be used for the ACT-FM scores and therapist response time to summarise therapist fidelity.
- **Treatment completion:** The number of sessions completed (ranges 0-8) by each participant will be used to explore if these have any influence on treatment outcomes. Descriptive statistics will be used to summarise the number of sessions completed.
- **Psychological flexibility:** The CompACT scores (total score and subscale scores) will be analysed to determine if changes from 0 to 12 week and 0 to 24 weeks influence outcomes at each time point. It is hypothesised that greater psychological flexibility is associated with better clinical outcomes.

A correlation analysis will be conducted for intervention arm to explore any association of primary outcome (i.e., GAD-7) with therapist fidelity, number of sessions completed and change in psychological flexibility separately.

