5.1.1 Explanation for choice of comparators

The treatment-as-usual (TAU) condition will be used to evaluate if iACT4CARERS offers an improvement over current practice. Participants in either group will continue to receive any routine support, such as Admiral Nurse appointments, during the trial. They will not be discouraged from seeking treatment outside of the study for ethical reasons. TAU will be monitored, and we will undertake additional exploratory data analysis to assess the impact of contamination if a substantial proportion of participants have used pharmacological or psychological therapies (further described in the data analysis section).

5.2 **Objectives**

This study aims to undertake a definitive RCT with an internal pilot phase to determine the clinical and cost effectiveness of iACT4CARERS plus TAU compared to TAU alone in family carers of people with dementia who present with anxiety symptoms.

Primary hypothesis

• iACT4CARERS plus TAU will be superior to TAU alone in improving anxiety symptoms in family carers of people with dementia at 12 weeks post-randomisation.

Secondary hypotheses

- iACT4CARERS plus TAU will be superior to TAU alone in improving anxiety symptoms over a 24week follow-up period.
- iACT4CARERS plus TAU will be superior to TAU alone in improving other mental health outcomes (e.g. psychological flexibility, depression) over 12-week and 24-week follow-up periods.
- iACT4CARERS plus TAU will be superior to TAU alone in terms of cost-effectiveness (cost per QALY).

This study also aims to assess fidelity and quality of implementation, establish causal mechanisms and identify contextual factors associated with variation in outcomes using the process evaluation approach.

Research questions for the process evaluation

- How is the delivery of iACT4CARERS achieved (fidelity and dose)?
- Are there any adaptations required to deliver iACT4CARERS as intended (adaptations)?
- To what extent can iACT4CARERS reach its intended service users (reach)?
- What are the mediating factors and context that may influence implementation and outcomes (mechanisms and context)?

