7.1 Outcome definitions

7.1.1 Primary outcome

The primary outcome is anxiety symptoms as assessed by the Generalized Anxiety Disorder-7 (GAD-7 [16]) at 12 weeks. In addition to the Mean (and SD), the proportions of participants falling into different severity ranges (mild, moderate, severe) at each time point will be reported.

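### The SAP 7.4 correlation of CompACT change with GAD-7 states no baseline adjustment and no allowance for therapist-level ACT-FM scores, so a real association can be masked or appear with the wrong sign

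*SAP*

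**What the plan says.** SAP 7.4 opens: "The following exploratory analyses will be carried out considering factors that may influence the finding". For CompACT, total and subscales, it says that these "will be analysed to determine if changes from 0 to 12 week and 0 to 24 weeks influence outcomes at each time point", and the stated hypothesis is: "It is hypothesised that greater psychological flexibility is associated with better clinical outcomes". The method comes in one closing sentence: "A correlation analysis will be conducted for intervention arm to explore any association of primary outcome (i.e., GAD-7) with therapist fidelity". The same sentence adds two further factors, sessions completed and CompACT change, each to be examined on its own. No covariate, model or clustering term is named.

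Other relevant places:

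- SAP 7.1.1: "The primary outcome is anxiety symptoms as assessed by the Generalized Anxiety Disorder-7 (GAD-7". The timing given there is 12 weeks, so this is a score level at a visit and not a change.
- SAP 7.4: ACT-FM gives scores for each therapist, whereas response time is recorded per participant and session. Protocol 6.1.1 plans at most 20 sites with 36 therapists.
- Protocol Table 2: CompACT is collected at baseline, 12 and 24 weeks. Only STTS-R is marked as treatment arm only.
- SAP 7.2: CompACT is compared between arms as a secondary outcome, with its baseline value in the model. The GAD-7 model has a random intercept for therapist within site.
- Protocol 5.2 sets out to "establish causal mechanisms and identify contextual factors associated with variation in outcomes using the process evaluation approach". Section 5 of the SAP says that the process evaluation is done separately and is not described there.

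**The concern.** The analysis sets a change score against an outcome level. CompACT change depends on where a carer started, and so does follow-up GAD-7. If low flexibility goes with high anxiety at baseline, carers with most room to gain flexibility are also those who tend to score higher on GAD-7 later. That alone produces a positive correlation between flexibility gain and later anxiety, whereas the SAP's hypothesis implies a negative one. A true association could therefore be hidden, or a null one reported with the wrong sign.

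Two smaller points belong with this. The sessions correlation has the same gap, because initial anxiety may be related both to how many sessions are completed and to later GAD-7. ACT-FM values are shared by all participants of a therapist, so a participant-level test that ignores therapist overstates its precision.

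At stake is how a secondary, exploratory statement about psychological flexibility is read, not the effectiveness result.

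**Working it through.** **Expected sample size.** The plan states no figure for the correlation, so its n comes from the trial calculation. With d = 0.35, two-sided 5% and 90% power, n per arm = 2 × (1.960 + 1.282)² / 0.35² = 171.6, or 172; the t-test version gives 172.5, so 173, as planned. Then 173 / 0.7 = 247.1, so 248 per arm and 496 in total, also as planned. The intervention arm would supply about 248 × 0.7 = 174 carers. By Fisher's z, |r| must exceed tanh(1.96 / √171) = 0.149 for 5% significance.

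**Model.** All values below are assumptions; the documents give no correlations. Scores are standardised within the arm, with equal CompACT variance at both visits:

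- corr(baseline GAD-7, baseline CompACT) = -ρ
- CompACT change: dC = -k × baseline CompACT + noise, so Var(dC) = 2k
- 12-week GAD-7 = λ × baseline GAD-7 - θ × dC + noise, where θ is the true link in SD per SD

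Then cov(GAD-7 at 12 weeks, dC) = λkρ - 2kθ, and r = (λkρ - 2kθ) / √(2k). The sign is wrong whenever θ < λρ/2.

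**Central case** (ρ = 0.5, λ = 0.6, k = 0.4; √0.8 = 0.894):

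| True θ | Unadjusted r | Slope adjusted for baseline GAD-7 and CompACT (simulation, 1,000,000 draws) |
|---|---|---|
| 0 | 0.12 / 0.894 = +0.134 | 0.00 |
| 0.1 | 0.04 / 0.894 = +0.045 | -0.10 |
| 0.2 | -0.04 / 0.894 = -0.045 | -0.20 |

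**Range** (ρ 0.3 to 0.6, λ 0.5 to 0.7, k 0.3 to 0.5):

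- θ = 0: r runs from √0.15 × 0.15 = +0.06 to √0.25 × 0.42 = +0.21. With n = 174, the chance of a significant result in the wrong direction is 12% to 80%.
- The sign changes at θ = 0.5 × 0.3 / 2 = 0.075 up to 0.7 × 0.6 / 2 = 0.21.
- θ = 0.3: r is negative throughout, -0.07 to -0.23. The partial correlation given baseline GAD-7 is -0.25 to -0.39.

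**Check without the model.** With r11 = corr(GAD-7 at 12 weeks, CompACT at 12 weeks), r10 = corr(GAD-7 at 12 weeks, baseline CompACT), rc = corr(baseline CompACT, CompACT at 12 weeks) and s = the 12-week to baseline SD ratio of CompACT, r = (r11 × s - r10) / √(1 + s² - 2 × s × rc). Taking r11 = r10 = -0.5, rc = 0.6 and s = 0.85 gives 0.075 / 0.838 = +0.09. Taking r11 = -0.6, r10 = -0.4, rc = 0.6 and s = 1 gives -0.2 / 0.894 = -0.22, the expected sign.

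**What adjustment does not remove.** In the central case with θ = 0, add an unmeasured common cause of both 12-week scores with loading 0.2, 0.3 or 0.4. The unadjusted r becomes +0.09, +0.04 and -0.04, and the adjusted slope -0.06, -0.14 and -0.25.

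**ACT-FM.** If 174 carers are spread evenly over 36 therapists, the mean cluster is 174 / 36 = 4.83 and effective n = 174 / (1 + 3.83 × ICC). Assumed ICCs of 0.01, 0.05 and 0.10 give about 168, 146 and 126.

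**The case against.** The section is headed exploratory, and its hypothesis and closing sentence speak of association; only the CompACT bullet's reference to influence goes further. The absence of adjustment is read from silence, since the SAP does not rule out a partial correlation. Limiting the sessions and fidelity analyses to the intervention arm is unavoidable, because TAU has neither. The randomised effect on CompACT is estimated in SAP 7.2, so the control data on that measure are not wasted. The sign reversal needs a weak true link or shrinking CompACT variance, and a shared 12-week mood component can cancel it. All of this stands, and it limits the point to an exploratory analysis. It does not justify leaving the adjustment unspecified in a prespecified plan when both baseline scores are already collected.

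Three stronger readings are tempting, and the documents do not support them:

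- *That this correlation is how the trial means to establish causal mechanisms.* Protocol 5.2 assigns that aim to the process evaluation, Protocol 6.5.3 gives interviews as the source for mediating factors, and section 5 of the SAP keeps that work outside the SAP.
- *That the ACT-FM analysis has an effective sample of 36.* By the formula above, this is true only at a therapist ICC of 1. Response time is not a therapist-level score at all.
- *That 0 to 24 week CompACT change is set against 12-week GAD-7.* The text refers to outcomes at each time point, which reads naturally as matched visits. It is unclear, because the closing sentence names only the primary outcome, but the cross-pairing is not stated.

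**Conclusion.** The point holds as a shortcoming of specification in an exploratory analysis. As written, the CompACT correlation mixes any true association with the effect of baseline severity. Under the assumed ranges it is biased towards the positive: +0.06 to +0.21 with no true link, positive for any link below 0.075 to 0.21 SD per SD, and correctly signed but attenuated at 0.3. These sizes rest wholly on assumed correlations and on equal CompACT variance at both visits. An unmeasured common cause would push the other way and could offset the bias. The loss of information in the ACT-FM analysis is modest at the ICCs tried, but a participant-level test that ignores therapist would still be too precise. Neither the primary analysis nor the between-arm comparison of CompACT is affected.

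**What to change.** In SAP 7.4:

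1. Replace the simple correlation for CompACT with a regression (or partial correlation) of follow-up GAD-7 on CompACT change, adjusted for baseline GAD-7 and baseline CompACT. State that change and outcome are taken at the same visit: 0 to 12 weeks with 12-week GAD-7, and 0 to 24 weeks with 24-week GAD-7.
2. Adjust the sessions analysis for baseline GAD-7.
3. Analyse ACT-FM scores with a therapist random effect, or at therapist level.
4. Describe all results as associations and remove the wording about influence.

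Optionally, because CompACT is collected in both arms, add an exploratory two-arm mediation model with 12-week CompACT as mediator and 24-week GAD-7 as outcome, stating the assumption of no unmeasured mediator-outcome confounding.

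The cost is revised wording and a little extra analysis on data already scheduled. The limit should be stated in the SAP: baseline adjustment removes the artefact of starting level but does not make the estimate causal.
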